## 7b Interim analyses and stopping guidelines - when applicable

NONE

# Randomization

---

8a Sequence generation,

9 Allocation concealment mechanism

10 Implementation

During the trial period 64 waiting list patients per month in 4 months will be allocated.  
The patients are 1:1 computer randomized to trial/control group.

See also 11a.

---

## 8b Type of randomisation; details of any restriction (such as blocking and block size):

NO RESTRICTIONS.

---

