### 3a Trial Design

This is a randomized clinical trial in which individual waiting list patients are allocated 1:1 into intervention group and control group.

---

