## 5 Intervention

Based on the theories and research mentioned above *patients in the intervention group* will be invited to join a group-based 6 hour *Thoughtful* course (8 patients per group). *Two delivery models will be tested:*

- A: 2 hour session per day - 3 days in a row in one week.
- B: 1 day 6 hour course.

Audios from the web-program and an illustrated book with core concepts & themes are demonstrated. Everything lectured can be reviewed at home by participants in greater details in the Audios and the book.

In group A patients are offered an individual session 1 month after the course.  
Group B patients are offered individual session when needed.

The course has been approved by the University Hospital as a documented treatment equated with other standard treatments.

The *Thoughtful* course is an *educational* course where participants are offered research-based knowledge in daily language about thinking. So patients can participate without telling anything about their personal challenges - just be present - anonymous - listen - and think. Naturally they are welcome to tell and ask - but it is not a requirement. In the hour immediately after each session participants are offered a short individual talk if needed. Pilot experiences show that participants are comfortable with this approach.

All patients enrolled in the trial - in the intervention group and in the control group - will keep their position on the waiting list and will have access to individual assessment and treatment as usual. So the *Thoughtful* intervention is a *supplemental* effort which does not affect standard procedures or patient legal rights.

Patients who are not able to join the group course because of social anxiety or practical reasons will be given course materials for self study and they will be offered individual introduction.

This delivery model has several advantages:

- In the *Thoughtful* program knowledge is presented in an illustrated book and in sound files (Audios) which makes it possible for people who don't read to join anyway. People who don't want to talk about their thoughts and feelings - who are not comfortable about sharing their burdens with others - can also join - that is self-treatment.

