## 7a Sample size

The total number of contact/treatment days in the centre (out-patient clinic, inpatient ward and emergency team) in 2021 was 14.621 = 1250 contact days per 100 patients.

Based on a standard deviation of 100 days, Type 1 error level of 5%, a 5% expected reduction of total number of contact days per year in the intervention group, we will need 64 patients in the intervention group and 64 patients in the control group in order to obtain a statistical power of 0,80.

Currently around 300 patients are on waiting list. Prioritizing long waiting time we enroll and randomize 256 patients in the trial:

- 64 patients in trial group A (3-day course) & 64 patients in control group A.
- 64 patients in trial group B (1-day course) & 64 patients in control group B.

So we expect this to be a reliable study with acceptable statistical power.

---

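### Unrestricted 1:1 randomisation will rarely give the 64/64 arms listed for each delivery model; drawing each monthly list exactly 32/32, balanced on prior contact days, would cost little

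*Protocol*

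**What the plan says.** - Section 3a (Trial Design): "individual waiting list patients are allocated 1:1 into intervention group and control group".
- Randomization section (items 8a, 9 and 10): "During the trial period 64 waiting list patients per month in 4 months will be allocated", and "The patients are 1:1 computer randomized to trial/control group".
- Section 8b, whose heading asks about blocking and block size, answers "NO RESTRICTIONS".
- Section 7a (Sample size) lists the arms as "64 patients in trial group A (3-day course) & 64 patients in control group A" and "64 patients in trial group B (1-day course) & 64 patients in control group B", 256 patients in all. It does not call these numbers expected or approximate.
- Section 5 (Intervention) runs the course with "8 patients per group", and gives self-study material to those who cannot attend.
- Section 12a names ANOVA without listing model terms.

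No section says how a patient or a month is assigned to model A or model B.

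**The concern.** An exact split is itself a restriction. If the computer forces 64/64, section 8b misdescribes the method. If it does not, section 7a describes arm sizes that the method will seldom produce. The allocation cannot be programmed unambiguously from this text, all the more because the route into A or B is missing.

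There is also a missed opportunity. Simple randomisation is the natural choice when patients arrive one at a time and a balanced sequence might be guessed. Here 64 patients are allocated per month from an existing waiting list, so each list can be drawn in one run and no next allocation exists to be predicted. Prior contact days should be obtainable from the patient record that supplies the primary outcome, so balance on them could be had for little effort. What is at stake is consistency and some precision.

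**Working it through.** **Inputs.** Allocation 1:1 with no restriction (sections 3a and 8b); 64 patients per month for 4 months (Randomization section); 64/64 in A and 64/64 in B, type 1 error 5%, power 0.80 (section 7a). Two-sided testing is assumed, since the protocol does not state it.

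**The plan's own figure.** A two-sample t-test with standardised difference 0.5 needs 63.8, so 64 per arm, and has power 0.801 at 64/64. The 0.5 is not a stated input. The stated inputs, read as 5% of 1250 days (62.5) with SD 100, give 2 × (1.960 + 0.842)² / 0.625² = 40.2, so 41 per arm. That mismatch is a separate matter. The value 0.5 is used below only because it is what 64 per arm implies.

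**Arm sizes under simple randomisation.** Let X be the number allocated to trial among N patients, X ~ Binomial(N, 0.5), with SD √(N/4).

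| Event | Result |
|---|---|
| 64/64 in one delivery model (N = 128) | 0.0704 |
| 64/64 in both models | 0.0704² = 0.0050 |
| SD and 95% range of one arm (N = 128) | 5.7; 53 to 75 |
| 32/32 in one month (N = 64) | 0.0993 |
| 32/32 in all four months | 0.0993⁴ ≈ 0.0001 |

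**Cost of unequal sizes.** Precision depends on n₁n₂/(n₁+n₂). At 64/64 this is 64 × 64 / 128 = 32.0; at 53/75 it is 53 × 75 / 128 = 31.1. With standardised effect 0.5, t-test power is 0.801 at 64/64, 0.790 at 53/75, and 0.798 averaged over the binomial distribution.

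**Possible gain from prior use.** If prior contact days correlate r with the outcome and enter the model as a continuous covariate, the residual SD shrinks by √(1 − r²), so the effective standardised difference is 0.5/√(1 − r²). With 64 per arm (t-test approximation):

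| Assumed r | Effective difference | Power |
|---|---|---|
| 0 | 0.500 | 0.80 |
| 0.3 | 0.524 | 0.84 |
| 0.5 | 0.577 | 0.90 |
| 0.7 | 0.700 | 0.98 |

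The protocol gives no correlation, so these values are assumptions. A two-level stratum keeps only part of the information. For a median split of a normally distributed covariate, r is multiplied by √(2/π) = 0.798, and power becomes 0.82 at r = 0.3 and 0.92 at r = 0.7. Contact days are unlikely to be normal, so this is only a guide.

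**The case against.** The best defence is that 64/64 stands under the sample size heading, where planned numbers belong, and that unrestricted 1:1 allocation has expectation 64/64. One could also read the Randomization section as drawing a random half of each monthly list, which would satisfy section 8b in the sense of no blocks and no strata. This stands in part: the text is ambiguous rather than irreconcilable, and a sentence would settle it. It does not remove the point, because the protocol says neither that the numbers are targets nor that half of each list is drawn.

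It is also right that the size imbalance does almost no statistical harm.

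Three stronger readings are tempting, and the protocol does not support them.

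- **Conflict with course groups of 8.** A reader might infer a cap of 32 seats a month and compute a 45% chance of exceeding it in a given month (91% in at least one of four), with informal reallocation to follow. Section 5 gives a course format. It states no number of courses and no cap, and it sends some patients to self-study. Even an exact 32 would not guarantee full groups, and nothing in the text suggests reallocation.
- **Bias from chance imbalance in prior use.** With an assumed SD of prior use of 10, 25 or 50 days, the standard error of the difference between arms of 64 is SD × √(2/64) = 1.8, 4.4 or 8.8 days, against a planned effect of 5% of 12.5 = 0.625 days per patient. That looks alarming, but chance imbalance is not bias, and the standard error of the analysis already allows for it. It reaches the outcome only as far as prior use predicts later use.
- **An unadjusted analysis.** Section 12a neither includes nor excludes covariates. Model terms may be in an analysis plan that is not shown, so their absence is no fault here.

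**Conclusion.** The point holds as one of consistency and cheap improvement. As written, section 8b delivers the arms listed in section 7a with probability 7.0% for one delivery model and 0.5% for both, so 64/64 can only be an expectation. The loss from unequal sizes is about one power point or less. The possible gain from using prior contact days ranges from small to substantial (0.80 to between 0.84 and 0.98 with a continuous covariate), but it rests on assumed correlations of 0.3 to 0.7 and on the implied effect of 0.5.

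The binomial figures rest on reading section 8b literally. The proposed draw assumes that the individuals on each monthly list are known when it is randomised. The protocol states only the batch size, but the existing waiting list of around 300 makes this a fair inference.

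**What to change.** In section 8b, replace the present answer with a rule of this kind: each monthly list of 64 is randomised in one computer run to exactly 32 trial and 32 control, stratified by contact days in the previous 12 months from the patient record (two levels), with a stated rule for strata of odd size so that the total stays at 32/32.

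State how patients or months are assigned to A or B. If each model takes two whole months, 32/32 per month gives 64/64 in each model. Delivery model should then not be a stratum within the month, and it is confounded with calendar month. If both models run in the same month, stratify by model within that month.

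Include the randomisation batch and prior contact days in the primary ANOVA, in the protocol or in the analysis plan, with prior days preferably as a continuous covariate.

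If simple randomisation is kept, say in section 7a that 64/64 are expected numbers and still state the A/B assignment.

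The cost is a few sentences and a change to the randomisation program. The one small downside is that prior-use data must be extracted before allocation. Because each list is drawn at once, the exact split makes no next allocation predictable.

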## 11a Blinding

It is not possible in this kind of intra-clinic research to completely blind either patients or therapists. For legal reasons individual treatment plan & course must be described in the electronic patient record. There is also an unavoidable risk that individual patients in the trial groups - or therapists - will talk about eventual Thoughtful program experiences - which may potentially "contaminate" control group patients with Thoughtful knowledge. The size of this risk is probably proportional to perceived benefit. A consequence may be a lowering of effect size.

Moreover the program is freely accessible on the internet - although the Norwegian version is only published shortly before trial start. The reason for this open access approach is that a log-in procedure is considered to be a major obstacle for vulnerable psychiatric patients. From an ethical perspective we also consider that open access to *vital knowledge about life-threatening thoughts* is crucial - for patients and for their primary supportive social network.

---

## 12a Statistical methods

ANOVA will be used for the statistical analysis.

---

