- Patients with for instance social anxiety and/or low mental energy level who have difficulties joining standard talking-therapy will in this way have access in a home setting to research-based self-treatment knowledge and training-tools. They can repeat the lectures any number of times and at times which suits them best. They can study alone or in companion with relatives or friends who support them.

- High fidelity is inherent in this kind of program as the material presented in book and audio files remains the same no matter how many times it is used and it is independent of variations in therapist approaches. The content of the intervention can be shared widely exactly as tested in randomized control trials.
- *Thoughtful* is a modular user-driven program. Research indicates that modular user-driven programs may have double clinical efficacy compared with standard delivery models (Weisz 2012).
- Research indicates that self-help materials supplemented by professional guidance may reduce symptoms in comparison to waiting list or control treatment and may produce comparable outcomes to formal therapist-delivered psychological therapies. Self-help concepts may thus have utility as a first step in treatment (Perkins 2009).

In the current trial the web-based program is combined with options for direct professional contact. Thus the individual patient can tailor the intervention to his/her own needs and circumstances.

---

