## 6a Outcomes

Primary outcome will be *use of mental health hospital services* measured by the number of contact/treatment days to the centre (in-patient, out-patient and emergency team contacts) in a 12 month follow up period from the day of intervention start. This outcome measure is considered to have a high face validity and to be a reliable proxy measure for patient wellbeing when applied within a consistent organizational context (Burns 2007, Addington 2012).

Secondary outcomes will be:

- Average change in score *before and 6 months after* intervention on a 3 item anonymous mental wellbeing questionnaire - see Appendix 1.
- Medication level based on pharmacy data.

The use of standard patient record data as outcome measures is in line with the Recommendation on Criteria for Establishing Strong Evidence of Effectiveness from a National Academies Report (O'Connell 2009).

A trial group sample of participants will be interviewed for a qualitative research study.

---

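### Section 12a names only ANOVA, with no course term, although only the intervention arm is taught in courses of 8; if courses differ, the interval is somewhat too narrow (minor)

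*Protocol*

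**What the plan says.** Section 3a makes the patient the unit of randomisation: "individual waiting list patients are allocated 1:1 into intervention group and control group". Section 5 then teaches intervention patients together, in a "course (8 patients per group"), under delivery model A or B. Controls receive usual care and no course. Intervention patients who cannot join a group "will be given course materials for self study and they will be offered individual introduction". Section 7a plans 64 intervention patients and 64 controls for each model.

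The whole of section 12a is "ANOVA will be used for the statistical analysis". Neither it, section 7a nor the section on subgroup analyses mentions course group, an ICC or a design effect. The subgroup section expects to analyse A and B separately.

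**The concern.** The design is partially nested: one arm is grouped into courses after randomisation and the other is not. Patients who share a course may share part of its effect, through the teaching, the questions raised or the mix of participants. Their outcomes are then positively correlated. An ANOVA that treats all patients as independent attributes too little variance to the intervention mean. The estimated difference between arms stays unbiased, but its standard error is too small, the interval too narrow and the type I error above 5%. If courses do not differ, nothing is lost and ANOVA keeps its level.

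**Working it through.** **Inputs from the protocol.** Course size m = 8 (section 5). 64 v 64 per delivery model (section 7a), so 64/8 = 8 courses per model and 16 in all if everyone attends. Type I error 5% (section 7a), taken as two-sided.

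**Assumed, because the protocol gives neither.** The ICC, over 0.0025 to 0.10, and the share f of the intervention arm taught in courses (1 or 0.75).

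The plan has no clustering figure to reproduce. Its 64 per group is taken as given. That number does not follow from section 7a's inputs: a reduction of 62.5 (5% of 1250) with SD 100 needs 41 per arm, and 64 fits a difference of half an SD. This is a separate matter. The ratios below involve neither the SD nor the effect.

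**Formulas.** Design effect in the intervention arm: DE = 1 + (m − 1) × ICC × f. In the control arm it is 1. With equal arms, the true variance over the ANOVA variance is v = (DE + 1)/2. The ANOVA standard error is too small by 1 − 1/√v, and the type I error is 2[1 − Φ(1.96/√v)].

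| ICC (assumed) | DE, f = 1 | v | SE too small by | Type I, f = 1 | Type I, f = 0.75 |
|---|---|---|---|---|---|
| 0.0025 | 1.0175 | 1.009 | 0.4% | 5.1% | 5.1% |
| 0.01 | 1.07 | 1.035 | 1.7% | 5.4% | 5.3% |
| 0.05 | 1.35 | 1.175 | 7.7% | 7.1% | 6.5% |
| 0.10 | 1.70 | 1.350 | 13.9% | 9.2% | 8.1% |

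**Number of courses.** It does not enter v. Simulation (20,000 runs, normal outcome) agrees. At ICC 0.01 / 0.05 / 0.10 the ANOVA type I error was 5.3% / 7.2% / 9.1% with 8 courses and 5.4% / 7.3% / 9.4% with 16.

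**Alternative analysis.** Standard errors clustered by course, CR2 with Satterthwaite degrees of freedom, each control its own cluster. Simulated with 8 courses of 8 v 64 (20,000 runs, normal outcome, about 25 degrees of freedom):

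| ICC | ANOVA type I | CR2 type I | CR2 interval width / ANOVA width |
|---|---|---|---|
| 0 | 5.0% | 5.0% | 1.03 |
| 0.0025 | 4.9% | 4.7% | 1.04 |
| 0.01 | 5.3% | 4.9% | 1.05 |
| 0.05 | 7.2% | 5.2% | 1.12 |
| 0.10 | 9.4% | 5.5% | 1.20 |

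With 16 courses v 128 (10,000 runs) at ICC 0 / 0.01 / 0.05, CR2 gave 5.0% / 4.9% / 5.3% and width ratios of 1.01 / 1.03 / 1.10. With a skewed outcome (exponential, 8 courses) at ICC 0 / 0.01 / 0.05, ANOVA gave 5.1% / 5.5% / 7.1% and CR2 5.0% / 5.0% / 5.2%.

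**Baseline adjustment.** Let r be the correlation of prior contact days with the outcome (assumed). Width of the adjusted CR2 interval over the unadjusted ANOVA interval, 8 courses, 1,500 runs:

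| r | 0 | 0.2 | 0.3 | 0.4 | 0.5 |
|---|---|---|---|---|---|
| ICC 0 | 1.035 | 1.018 | 0.993 | 0.954 | 0.896 |
| ICC 0.01 | 1.055 | 1.034 | 1.010 | 0.967 | 0.920 |

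Break-even is near r = 0.3.

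**The case against.** **It belongs in an SAP.** ANOVA can hold a nested course factor, nothing in 12a forbids one, and an SAP that is not shown could add it. That is true and is one reason to rank the point low. But 12a states a method without deferring the model to another document, and the delivery described in section 5 calls for one more term.

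**The ICC is probably low.** Section 5 says of the book and audio content that "it is independent of variations in therapist approaches" and that "patients can participate without telling anything about their personal challenges"; the self-study route dilutes clustering further. This stands as a reason to expect a low ICC, not a zero one. The course is also taught live, and participants may speak and ask questions.

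**The remedy can cost more than the defect.** This stands at low ICC. At ICC 0.01 the correct standard error is 1.7% larger than the ANOVA one (√1.035 = 1.017), while the CR2 interval is 5% wider with 8 courses and 3% wider with 16. The benefit appears at ICC 0.05 and above.

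**A reader might infer that section 7a itself fixes a small ICC.** From "1250 contact days per 100 patients" one gets 12.5 days per patient and a planned effect of 0.625 days. If courses differed by an SD as large as that effect, the ICC would be (0.625/SD)²: 0.01 / 0.0025 / 0.0006 for an assumed per-patient SD of 6.25 / 12.5 / 25 days, and 0.00004 if the stated SD of 100 is per patient. The answer depends on an SD whose scale is unclear and on a between-course spread that the protocol never gives. Section 7a therefore supports no particular ICC.

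**Conclusion.** The point holds as a minor one. The protocol describes courses of 8 in one arm only and names an analysis without a course term. The consequence is conditional on courses differing: the estimate is unbiased, and the standard error is 1.7% / 7.7% / 13.9% too small at an assumed ICC of 0.01 / 0.05 / 0.10, with a type I error of about 5.4% / 7.1% / 9.2%. It is smaller with self-study and negligible at ICC 0.01 or below.

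Two stronger readings are not supported. One is that the separate A and B comparisons suffer most because each rests on about 8 courses. The inflation depends on course size, ICC and the share taught in groups, so it is the same for A, B and the pooled comparison; fewer courses only make the clustered analysis dearer. The other is that the planned ANOVA is invalid or the result biased. With no ICC in the protocol, and features that point to a low one, that cannot be said.

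**What to change.** In section 12a, write for example:

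> Contact/treatment days over 12 months are compared between arms as randomised, using a linear model with arm and, for precision, contact/treatment days in the 12 months before randomisation, taken from the same patient record. The pooled analysis also includes delivery model (A/B). Standard errors are clustered by course group attended, using CR2 with Satterthwaite degrees of freedom. Each control, each self-study patient and each intervention patient who attends no course is a separate cluster. The course-group number is recorded at delivery and included in the data extract.

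The last cluster rule is needed because section 5 only invites patients and section 4a declares intention to treat. Clustering changes the standard error, not the arm in which a patient is analysed.

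**Cost.** A few sentences, one field to record and one to extract. The outcome is already counted "in a 12 month follow up period from the day of intervention start", so start dates must be held anyway; noting the group number is simpler than rebuilding it from them. The statistical cost, before adjustment, is an interval about 3% wider with 8 courses (1% with 16) at ICC 0, and 5% wider (3% with 16) at ICC 0.01, which is more than the correction needed there. Baseline adjustment does not address clustering. It offsets this cost only if prior contact days correlate with the outcome at about 0.3 or more, a figure the protocol does not give.

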## 12. Subgroup analyses

Based on the sample size & power calculation we expect that it will be possible to analyse on the level of the two delivery groups A & B. It may be also be feasible to analyze the use of the 3 service subgroups in the center: Outpatient clinic, emergency team and inpatient ward.

